Current/present, worst, least, and average pain at the surgical site will be assessed using a Numeric Rating Scale (NRS) as part of the Brief Pain Inventory (short form). The Brief Pain Inventory is an approved NINDS common data elements Scale. The use of single items (e.g., average pain) in addition to the composite score is supported by the IMMPACT recommendations for assessing pain in clinical trials. The NRS will be recorded at all time points (**Table 2**), ***with the primary end point being the mean value of the “average” pain scores for postoperative days 0-7*** (see statistical section for further details). The NRS is a highly-sensitive measure of pain intensity with numbers

ranging from 0 to 10, zero equivalent to no pain and 10 equivalent to the worst imaginable pain. The NRS has been demonstrated to be a valid and reliable measure following analgesic interventions. In addition, NRS scores correlate well with other measures of pain intensity, and demonstrate high test-retest reliability. These NRS characteristics led to recent IMMPACT consensus recommendations for use of the 10-point NRS of pain intensity for pain trials.

An additional instrument, the Defense and Veterans Pain Rating Scale (DVPRS), will be utilized at various time points following surgery. The DVPRS was developed specifically for—and subsequently validated in—active duty military and Veteran patient populations. Unfortunately, this new instrument has not been validated for repeated measures, and therefore will not be used as a primary end point for the current investigation. However, future pain-related investigations involving military personnel and Veterans will undoubtedly use the DVPRS, and we want the results of the current study to be comparable. Therefore, we will use the DVPRS as a secondary end point at various time points (not all to lessen the questionnaire burden on subjects).

Primary end point: *In order to claim that percutaneous PNS is superior to usual and customary analgesia, at least one of Hypotheses 1 and 2 above must be superior while the other either superior or at least noninferior.*

Hypothesis 3 (UH3): Physical and emotional **functioning** will be significantly improved in the 12 months following ambulatory surgery with percutaneous PNS as compared with usual and customary analgesia (measured with the Brief Pain Inventory).

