We will first test for noninferiority of PNS to usual care on each of the two outcomes using 1-tailed noninferiority tests. The noninferiority deltas will be 1 point (worse) in pain score and 20% higher in opioid consumption. Noninferiority will be assessed at the overall 0.05 significance level with no adjustment to the significance criterion for testing two outcomes since noninferiority is required on both outcomes – i.e., an intersection union test. A noninferiority delta of 1 point in pain score is conservative since receiver operating characteristic curve analysis has demonstrated that changes from baseline of at least 1.7 along a 10-point NRS accurately identified patients who rated improvements as “much improved” or more, compared with those who perceived no change or worsening following analgesic interventions.^{153,156,177-179}

We will assess noninferiority on pain score using a one tailed t-test which incorporates the noninferiority delta of 1 point. The estimated treatment effect for pain score will be derived from a linear mixed effects model with the outcome of patient’s “average” pain score for each day, with fixed effects for intervention (PNS vs usual care) and time (days 1 through 7), and assuming an autoregressive correlation structure among and measurements on the same patient overtime. We will then test for noninferiority with a one tailed t-test in which the numerator is the estimated treatment effect from the model minus the noninferiority delta (1), and the denominator is the standard error of the estimated treatment effect. This method will yield results similar to comparing groups on the patient mean of these seven days, but is more flexible since it allows for missing data and also directly accounts for the correlation within patient. The model also allows assessing the treatment by time interaction, but this will most likely not be of interest.^{180,181}

Cumulative opioid consumption is not typically normally distributed, but usually approximates a log-normal distribution. We therefore plan to assess the treatment effect of PNS versus usual care on the log transformed cumulative consumption through POD 7 using a simple linear regression model (equivalent to a t-test). The estimated treatment effect (i.e., difference between groups) will then be used in a noninferiority test with null and alternative hypotheses as: $H_0: \mu_1 - \mu_2 \geq \log(1.2) =$

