Planning Phase sample size considerations. The sample size for the planning phase of 64 patients will be sufficient to estimate the treatment effects of interest with moderate precision, i.e., a confidence interval width of roughly 1.1 standard deviations for each outcome measure. Confidence interval width for a standard deviation estimate will be 0.70 standard deviations. The planning phase will be sufficient to use in estimating the expected treatment effect and standard deviation for each outcome for the larger trial.

UH3 Implementation Phase. Statistical methods for the UH3 Implementation Phase will follow very closely the methods described for the UG3 Planning Phase. The main difference is that UH3 Implementation Phase will have sufficient data to conduct the subgroup analyses and also considerably more power to assess the treatment effects of interest.

Another substantive difference from the planning phase is that in the full trial we will conduct interim analyses at each 25% of the planned enrollment using a group sequential method with gamma spending function and gamma parameter of -4 (quite conservative) for efficacy and 0 (moderately aggressive) for futility (**Figure 14**). The probability of crossing a boundary for either efficacy (mainly) or futility at the first through fourth looks would be 0.10, 0.42, 0.80 and 1.0, respectively, assuming the alternative hypotheses were true.

Figure 14. Stopping boundaries for 1-tailed tests for superiority for either pain score or opioid consumption. Blue region indicates superiority (reduced opioid consumption or pain score) and pink region indicates futility (lack of superiority). Z-statistic represents strength of evidence against the null hypothesis, either ratio of means or difference in means divided by standard error.

Missing outcomes data will be summarized along with the etiology of the absence. | While very little outcomes data is expected to be missing,

analyses will be intention to treat, and imputation of missing data using methods such as multiple imputation and last observation carried forward will therefore be utilized, based on the situation. In a conservative analysis imputation will involve the conservative approach of assigning the worst observed outcome to patients in intervention groups and best observed outcomes to those in control.

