Throughout, the significance level will be 0.05 for each hypothesis. SAS statistical software (Cary, NC) will be used for all analyses, and East 6.0 (Cytel, Inc. Cambridge, MA) for interim monitoring and sample size calculations.

UH3 Implementation Phase sample size considerations. Sample size parameters for the implementation phase will be derived from estimates in the planning phase. The sample size calculations below are conservative in that we observed a coefficient of variation for opioid consumption observed in our preliminary data of 0.48, substantially better than the assumed 0.65. It is thus quite possible that the actual sample size for the implementation phase will be smaller.

Sample size for the full trial will be chosen to allow an overall 90% power at the 0.025 significance level (since 1-tailed tests) to claim the intervention more effective than the control on postoperative opioid requirements and pain as measured by NRS pain score. In our joint hypothesis testing on these two outcomes, we power the study to have overall 90% power to detect superiority on either

outcome and at least noninferiority on both. We assume a coefficient of variation of 1.0 for opioid consumption and a standard deviation of 2 for pain score.

Power for the joint hypothesis testing will be driven by superiority tests since superiority is needed for at least 1 of the 2 outcomes. For cumulative opioid consumption through POD 3 our previous data had a coefficient of variation (CV) of 46% (mean (SD) of 28 (13) mg). Conservatively assuming a coefficient of variation of 75% through 7 days,¹⁸³ with a total N=528 we would have 90% power to detect a relative reduction of 20% in mean opioid consumption at the overall 0.025 significance level (0.0125 for each of the two 1-tailed tests for superiority), adjusting for interim analyses (N=448 before adjustment for interim analyses).

This sample size will yield high power (>0.95%) to detect superiority based on the intervention group having 1 point or more better than the control group on NRS pain score within the first 7 days, assuming a standard deviation of 2 points for mean of the “average” pain score for each patient.

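### Noninferiority is tested at one-sided 0.05 inside a superiority claim stated at 0.025, so the claim's false-positive rate can be twice the stated level

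*Combined protocol and SAP*

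**What the plan says.** All the relevant text is in section 9.

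- **Decision rule** (UH3 Implementation Phase, after Hypothesis 2; repeated in the statistical plan under UG3 Planning Phase): for a claim of superiority, "at least one of Hypotheses 1 and 2 above must be superior while the other either superior or at least noninferior".
- **Noninferiority tests** (statistical plan, UG3 Planning Phase): "We will first test for noninferiority of PNS to usual care on each of the two outcomes using 1-tailed noninferiority tests". The margins follow: 1 NRS point for pain and 20% for opioid use. Then: "Noninferiority will be assessed at the overall 0.05 significance level with no adjustment to the significance criterion for testing two outcomes". The reason given is that both must pass, an intersection-union test.
- **Carry-over** (statistical plan, UH3 Implementation Phase): "Statistical methods for the UH3 Implementation Phase will follow very closely the methods described for the UG3 Planning Phase". No separate noninferiority level is given for UH3.
- **Level of the claim** (UH3 sample size considerations): the trial is sized for "an overall 90% power at the 0.025 significance level (since 1-tailed tests) to claim the intervention more effective than the control". The same paragraph describes the joint rule, and the next one allots 0.0125 to each of the two one-tailed superiority tests.
- **General statement** (just before the UH3 sample size considerations): each hypothesis is tested at 0.05 throughout. Whether this is one- or two-sided is not stated.

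**The concern.** The plan's reason for using 0.025 is that its tests are one-tailed. That reason applies equally to the noninferiority tests, but they stay at 0.05.

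The intersection-union argument is sound as far as it goes. When both noninferiority tests must succeed, neither needs adjusting for the other. But a claim that needs several tests to succeed is only as strict as its most lenient required test. If PNS is clearly better on one outcome and truly at the margin on the other, the claim turns on a single noninferiority test, which errs 5% of the time.

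The noninferiority requirement exists to block a superiority claim when lower opioid use is paid for with worse pain, or the reverse. The stated 0.025 fails at the edge of that situation. The point concerns the level of one test at one look and does not depend on the interim analyses.

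**Working it through.** **Inputs from section 9.** Allocation 1:1; total N=528 (448 before the interim adjustment); opioid CV 0.75; planned opioid reduction 20%; pain SD 2; margins 1 point and a ratio of 1.2; superiority at one-sided 0.0125 per outcome; noninferiority at one-sided 0.05.

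**Assumptions.** The opioid margin is ln(1.2) = 0.1823 on the natural-log scale. The correlation between the two outcomes is not in the documents, so 0 and 0.5 are used. Error rates and power are for a single look.

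**Reproducing the plan's sample size.**
- Log-scale variance = ln(1 + 0.75²) = 0.4463, so SD = 0.668. Effect = ln(0.8) = −0.2231.
- N = 4 × 0.4463 × (2.241 + 1.282)² / 0.2231² ≈ 445, or 446 with equal arms. The noncentral-t version gives 448, as stated.
- Four equal looks with gamma −4 for efficacy and gamma 0 non-binding futility inflate N by 1.1787: 448 × 1.1787 = 528, as stated.

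CV 0.75 with one-sided 0.0125 per outcome is therefore the basis of the design.

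**Maximum error of the claim.** Superiority at 0.0125 on an outcome implies noninferiority on that outcome, so the rule reduces to superior on one and noninferior on the other. The required components have levels 0.025 (superiority on at least one), 0.05 (pain noninferiority) and 0.05 (opioid noninferiority). The maximum error is the largest of these, 0.05.

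A direct check for opioid use down 20% and pain exactly 1 point worse, correlation 0, N=528: power for opioid superiority at a single look is 0.945, so the false-claim rate is 0.945 × 0.05 = 0.047.

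**Simulated false-claim rates** (bivariate normal, 2 million draws, N=528):

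| Truth | Correlation | Noninferiority at 0.05 | Noninferiority at 0.025 |
|---|---|---|---|
| Opioid −20%, pain +1 | 0 | 0.0472 | 0.0238 |
| Opioid −20%, pain +1 | 0.5 | 0.0498 | 0.0248 |
| Opioid −30%, pain +1 | 0 | 0.0499 | 0.0249 |
| Pain −1, opioid ratio 1.2 | 0 | 0.0500 | 0.0252 |
| No effect on either | 0 | 0.0238 | 0.0234 |
| No effect on either | 0.5 | 0.0230 | 0.0230 |

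At N=448 and correlation 0, the first, third and fourth rows become 0.0451, 0.0499 and 0.0502 with noninferiority at 0.05.

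**Largest observed result still called noninferior, N=528.**
- Pain: SE = 4/√528 = 0.174. Limits: 1 − 1.645 × 0.174 = 0.71 at 0.05, and 1 − 1.96 × 0.174 = 0.66 at 0.025.
- Opioid: SE = 2 × 0.668/√528 = 0.0581. Limits: exp(0.1823 − 1.645 × 0.0581) = 1.09, and exp(0.1823 − 1.96 × 0.0581) = 1.07.

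**Power cost of moving to 0.025, N=528.**
- Joint claim, opioid −20% and no pain difference, correlation 0: 0.9455 before, 0.9453 after.
- Pain noninferiority with no true difference: above 99.9% at either level.
- Opioid noninferiority at a true ratio of 1: 0.1823/0.0581 = 3.136, so Φ(3.136 − 1.645) = 0.932 before and Φ(3.136 − 1.96) = 0.880 after.

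**The case against.** **The stated level is open to dispute.** The plan also says that each hypothesis is tested at 0.05 throughout. The 0.025 sits in a sample-size paragraph whose only explicit allocation is to the superiority tests. One could read the plan as 0.025 for superiority with a separate 0.05 noninferiority gate. Or one could read 0.05 as a two-sided convention that becomes 0.025 for any one-tailed test, in which case there is no excess error. Neither reading settles the matter. The general sentence gives no sidedness, the noninferiority text names one-tailed tests and 0.05 together, and the 0.025 is attached to claiming PNS more effective, not only to the superiority tests.

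**The 0.05 comes from the planning-phase text.** In UG3 the emphasis is on estimation, and the UH3 statistical section is due for revision after the pilot. That revision is described in terms of treatment effects and group means, however, and UH3 has no other noninferiority level.

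**The doubling is a boundary worst case.** This stands. If pain is truly 1.1 points worse, the rate is at most 1.3%, since 1.645 + 0.1/0.174 = 2.22. At 1.2 points worse it is at most 0.3%. Below 1 point, a noninferiority finding is not an error by the plan's own margin. The change in cutoffs is also small: 0.05 NRS points, and 1.09 to 1.07.

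**The cost depends on the CV.** This also stands. The plan separately mentions a CV of 1.0. At that value the log-scale SD is √ln 2 = 0.833 and the SE is 0.0725, so opioid noninferiority power at a true ratio of 1 falls from 81% to 71%. The plan also prints log(1.2) as 0.263, which is the base-2 value. Applied to natural-log data, that margin gives power of 99.8% and 99.5% and cutoffs of 1.18 and 1.16. The error rate at whichever margin is used does not change.

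**Conclusion.** The concern holds. As written, the joint claim has a maximum one-sided false-positive rate of 5%, against the 2.5% stated for it. The rate is 4.7–5.0% at N=528 when one outcome is at its margin and the other is better by 20% or more (opioid use) or by 1 point (pain). It stays at 2.3–2.4% when PNS has no effect on either outcome, so the stated level fails only in the mixed case that the noninferiority requirement is there to police. The error result rests on reading the noninferiority level as one-sided 0.05, which is the plain sense of the text, and on a single look. It does not depend materially on the assumed correlation.

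**What to change.** For UH3, state that each noninferiority test is run at one-sided 0.025. Equivalently, the upper limit of the two-sided 95% confidence interval must lie below 1 point for pain and below a ratio of 1.2 for opioid use. There should still be no adjustment between the two tests. The whole claim then has the 0.025 level given in the sample size considerations. If the sponsor prefers to keep 0.05 for noninferiority, it should state that the joint claim is made at one-sided 0.05. In either case, add the sidedness to the general 0.05 statement so that the three places agree, and do so before any unmasked UH3 results exist.

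This is a one-number edit and N does not change. Power for the planned 20% opioid reduction is essentially unaffected. The real cost falls where PNS improves pain but leaves opioid use unchanged: opioid noninferiority power at N=528 falls from 93% to 88% at CV 0.75, and from 81% to 71% at CV 1.0. The sponsor should look at that scenario when the CV is re-estimated from the pilot.

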For women of childbearing age with the possibility of pregnancy, a sample of urine will be collected before any study interventions to confirm a non-pregnant state [this is standard for the surgery regardless of study participation]. Study participation will require that women of childbearing age with the possibility of pregnancy use a birth control method, such as abstinence, diaphragm, condom or intrauterine device to prevent pregnancy until lead removal. Anthropomorphic and demographic characteristics as well as baseline end points will be recorded/measured, including a pain score at the surgical site using the Numeric Rating Scale (NRS, 0-10), sensory deficits (measured with von Frey filaments within the cutaneous distribution of the target nerve), and muscle strength (measured with a pressure transducer; **Table 1**).

Table 1. Anatomic locations for electrical leads and peripheral nerve blocks.

Surgical Location	Surgical Procedures	Lead Location	Peripheral Nerve Block Location	Muscle Motion/Strength Tested
Shoulder	• Rotator cuff repair	Brachial plexus roots	Brachial plexus trunks	Shoulder abduction and grip strength
Knee	• Anterior cruciate ligament repair with a patellar autograph	Femoral	Adductor canal	Knee extension
Foot or ankle	• Hallux valgus correction • Ankle arthrodesis/arthroplasty	Subgluteal sciatic	Popliteal sciatic	Plantar flexion

Figure 8. Study protocol

Lead insertion. Insulated leads will be inserted prior to peripheral nerve block administration. The lead insertion sites will be cleansed with chlorhexidine gluconate and isopropyl alcohol, and a sterile, fenestrated drape applied. A portable ultrasound paired with either a linear or curved array transducer within a sterile sleeve will be used for lead insertion (Figure 9). The target nerve will be imaged in a transverse cross-sectional (short axis) view and a local anesthetic skin wheal raised lateral to the ultrasound transducer.

A needle and a pre-loaded, monopolar, helically-coiled, insulated lead (SPR Therapeutics, Cleveland, OH) will be inserted. Using an in-plane ultrasound approach, the needle tip will be advanced to approximately 1-2 cm from the target nerve. The lead will be subsequently attached to an external stimulator (SPR Therapeutics), and a surface return electrode applied. Accurate lead placement will be confirmed with subject reports of comfortable sensations over the surgical site without eliciting muscle contractions.

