Randomization will be stratified by institution and anatomic lead location (**Table 4**) in a 1:1 ratio and in randomly chosen block sizes. Randomization lists for each enrolling center will be created by the Cleveland Clinic. Treatment group assignment will be conveyed to the enrolling sites via the same secure web-based system (RedCap) used to collect and collate all post-intervention endpoints (see “Data Collection” paragraph below). Stimulators are capable of programming to either (1) pass electrical current; or, (2) not pass electrical current. Importantly, these 2 modes (active and sham) are indistinguishable in appearance, and therefore investigators, subjects, and all clinical staff will be masked to treatment group assignment, with the only exception being the unmasked individual who programs the stimulator (and will not have direct contact with the subject). The unmasked personnel will have access to the randomization list on RedCap, program the stimulator appropriately (sham vs. active), and provide the investigator interacting with the study subject with the device without indicating the treatment group.

Subjects will be informed that often during postoperative active treatment with electrical current patients do not always have the sensations experienced during preoperative lead placement and once proper placement is confirmed with comfortable sensations, therapeutic levels of stimulation may be delivered sub-threshold (below the intensity required for sensation and still provide relief, which is factual/accurate). ***This protocol will ensure a randomized, double/triple-masked, sham/placebo-controlled trial.*** For the feasibility study (UG3), unmasking will occur 2 weeks following surgery to allow for protocol revisions, as necessary (“double masked” during data collection). In contrast, for the definitive pragmatic clinical trial (UH3) unmasking will not occur until statistical analysis for the entire investigation is complete (termed “triple masked”).

Intraoperative course. The primary surgical anesthetic will be a general anesthetic, spinal anesthetic (bupivacaine 0.5%) or exclusively the preoperative single-injection peripheral nerve block. Anesthetics that are also analgesics such as ketamine will not be used: the only permitted analgesic will be intravenous fentanyl, which will be minimal since all subjects will receive a single-injection peripheral nerve block immediately prior to surgery.

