Quarterly Total:	0	0	0	0	32	32	0	0	48	48	48	48	48	48	48	48	48	48	48	0	0	0	0	592	
Yearly Total:	0				64				192				192				144				0				

The Study Team (Figure 13). The study team consists of the Principal Investigator, 7 additional members of the Steering Committee, 7 Site Directors, 1 research coordinator for each of the 7 enrolling centers, and 2 Significant Contributors from the company that developed the electrical leads and stimulator.

Statistical Plan and Data Analysis

Randomized groups will be compared for balance on baseline characteristics using descriptive statistics and the standardized difference (i.e., difference in means or proportions divided by pooled standard deviation). Absolute standardized differences larger than 0.10 will be considered imbalanced and the corresponding variables considered for adjustment in all analyses. Primary analyses will be modified intent-to-treat, such that all randomized patients who receive at least some of the study intervention will be included in the analyses. All patients will be analyzed in the group to which they were randomized.

Statistical methods will largely be the same for the Planning Phase and the Implementation Phase. As explained below, one difference is that in the planning phase focus we will be on the estimated confidence interval for the treatment effects and the variability of the outcomes, as these will be used in designing the full trial. Another is that interim analyses and more thorough subgroup analyses will be done in the Implementation Phase. Details are given below.

UG3 Planning Phase. For Specific Aim 2 we will estimate the treatment effect of PNS versus usual and customary care on pain and opioid consumption using a joint hypothesis testing framework. Specifically, we will conclude PNS is superior to usual and customary analgesia, at least one of Hypotheses 1 and 2 must be superior while the other either superior or at least noninferior.

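### Randomisation is stratified by institution and lead location, but neither primary model includes them, and covariate adjustment is left to a chance-imbalance rule

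*Combined protocol and SAP*

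**What the plan says.** All of this is in Section 9 of the combined protocol and SAP.

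- **Randomisation** (Treatment group assignment): "Randomization will be stratified by institution and anatomic lead location". With seven centres and three lead locations, that is 21 strata.
- **Pain model** (Statistical Plan and Data Analysis): a linear mixed model on the daily average score "with fixed effects for intervention (PNS vs usual care) and time (days 1 through 7", with autoregressive correlation within patient.
- **Opioid model** (same section): log cumulative dose through day 7, compared "using a simple linear regression model (equivalent to a t-test".
- **Covariates** (opening paragraph of the same section): "Absolute standardized differences larger than 0.10 will be considered imbalanced and the corresponding variables considered for adjustment in all analyses". No covariate list follows, and nothing says how a flagged variable is accepted or rejected.
- **Full trial**: "Statistical methods for the UH3 Implementation Phase will follow very closely the methods described for the UG3 Planning Phase".
- **Masking**: in UH3, "unmasking will not occur until statistical analysis for the entire investigation is complete".

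Lead location reappears only in the subgroup analyses by anatomic site. Baseline measures are collected, "including a pain score at the surgical site using the Numeric Rating Scale (NRS, 0-10", but the pain model does not use them.

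**The concern.** Stratified blocking lowers the true variance of the treatment difference when the strata predict outcome. A model without the strata still counts between-stratum variation as noise, so its standard error is too large. Tests become conservative and confidence intervals too wide, for superiority and noninferiority alike. Analysing each location separately as a subgroup does not repair the primary standard error.

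The imbalance rule does not fill the gap. It responds to imbalance, which stratification removes, rather than to prognostic value. For every other baseline variable it fires by chance, and the step from flagged to adjusted is undefined. The primary model is therefore not fixed in advance. Masking the statisticians limits steering but does not specify a model.

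There is a possible knock-on effect. UH3 sample-size parameters are to come from the planning phase (UG3). If the outcome variability is taken from an unadjusted model, precision forgone in the analysis may turn into patients enrolled.

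**Working it through.** **Reproducing the plan's sample size.** The plan states that "with a total N=528 we would have 90% power to detect a relative reduction of 20% in mean opioid consumption", at one-sided 0.0125 per outcome with CV 75%, and gives 448 before interim adjustment.

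- Log-scale variance: ln(1 + 0.75²) = 0.446, so SD 0.668. Effect: ln(0.8) = −0.223.
- z(0.9875) + z(0.90) = 2.241 + 1.282 = 3.523.
- Total N = 4 × 3.523² × 0.446 / 0.223² ≈ 445. The t-based version gives exactly 448.
- Four looks with the stated spending functions give an inflation of 1.182, and 448 × 1.182 ≈ 530 against the stated 528.

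The sample size is reproduced, and it rests on an unadjusted comparison.

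**Effect of leaving out the strata (opioid outcome).** Let R² be the share of variance in log dose explained by the strata and k = √(1 − R²). The documents give no R², so 5%, 10% and 20% are assumed. At R² = 0 nothing changes.

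| Quantity | Formula | 5% | 10% | 20% |
|---|---|---|---|---|
| Actual size, nominal 0.0125 | 1 − Φ(2.241/k) | 0.0107 | 0.0091 | 0.0061 |
| Actual size, noninferiority 0.05 | 1 − Φ(1.645/k) | 0.0457 | 0.0415 | 0.0330 |
| Excess CI width | 1/k − 1 | 2.6% | 5.4% | 11.8% |
| Power, unadjusted | Φ(1.282/k) | 90.6% | 91.2% | 92.4% |
| Power, adjusted | Φ(3.523/k − 2.241) | 91.5% | 93.0% | 95.5% |
| N for 90%, unadjusted | 448 × [(2.241 + 1.282k)/3.523]² | 440 | 431 | 414 |
| N for 90%, adjusted | 448 × (1 − R²) | 426 | 403 | 358 |
| Difference in N | | 14 | 28 | 56 |

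**Simulation check** (seven sites, three locations; blocks of 2, 4 and 6 assumed). At N = 528 and R² of 0, 10, 20 and 30%, unadjusted size was 0.0122, 0.0078, 0.0070 and 0.0038. Size adjusted for site and location was 0.0119, 0.0114, 0.0142 and 0.0131 (Monte Carlo error about 0.001). Both agree with the theory.

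**Pain outcome.** Suppose within-patient correlation, given the strata, is AR(1) with rho 0.5 to 0.8. The nominal 0.0125 test then runs at about 0.007–0.008 for R² = 10% and 0.003–0.004 for R² = 20%. Power matters little here: for 1 point, SD 2 and N = 448, the standard error is 2 × √(4/448) = 0.189, and Φ(1/0.189 − 2.241) = 0.9989 even at R² = 0.

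**What the 0.10 rule flags.** For a non-stratified variable with n per arm, the chance is 2 × [1 − Φ(0.10/√(2/n))]:

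- UH3, 264 per arm: 25%.
- UG3, 32 per arm: 69%.
- UH3 looks at 66, 132, 198 and 264 per arm: about 57%, 42%, 32% and 25%. If the rule is applied at each look, the covariate set could change within one sequential test.

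For lead location, simulated stratified randomisations (Figure 12 site sizes; equal location mix and blocks of 2, 4 and 6 assumed) gave 0 flags in 4,000 UH3 trials. In UG3, with 64 patients over 21 strata, a given location was flagged in about 49% of trials and at least one location in about 78%. The same rule would tend to give different models in the two phases.

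**The case against.** The strongest reply is that nothing here is invalid. Type I error is not inflated, the estimate is not biased, the stated N is correct and the planned power is met. The size of the loss rests on an R² that the documents do not give; at 5–10% the gain from adjusting is only 0.9–1.8 percentage points of power. That stands, and it limits the weight of the point.

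The effect on the overall claim is smaller still. Success needs superiority on one outcome and at least noninferiority on the other. If both design effects hold at N = 448, pain superiority has power 0.9989. Opioid noninferiority exceeds 0.9999: the log-scale standard error is 0.668 × √(4/448) = 0.063, and (ln 1.2 + 0.223)/0.063 = 0.405/0.063 is about 6.4, against a critical value of 1.645. The joint claim is then above 0.998 unadjusted. The loss matters for that claim mainly if PNS reduces opioid use but has little effect on pain. This also stands. Interval width and the opioid result in its own right are still affected.

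Two further replies carry less. First, flagged variables are only considered for adjustment, so a 25% flag rate is not a 25% entry rate. That is true, but the missing decision rule is itself part of the problem. Second, the plan schedules a revision of the UH3 statistical section after UG3. The text there speaks of the treatment effect and group means and does not promise adjustment for the strata.

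On baseline pain, the pain endpoint is defined over days 0–7 while the model uses days 1–7. A day-0 score is not an outcome in the model as written, but the two statements should be aligned before it is used as a covariate.

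**Conclusion.** The point holds. The strata used for randomisation are missing from both primary models, and the only route to adjustment is a rule that will practically never select them in UH3 and that fires for other variables by chance.

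The consequence is conservatism and lost precision, conditional on the strata being prognostic: for an assumed R² of 5–20%, 14 to 56 patients on the fixed-sample base of 448 and opioid confidence intervals 2.6–11.8% too wide. If the strata are not prognostic, this part disappears, but the covariate set remains unspecified. Omitting baseline pain costs precision only and does not misstate the standard error; no figure can be put on it from the documents. This is a worthwhile improvement to a valid analysis, not a flaw that threatens the trial's conclusions.

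**What to change.** 1. Name lead location (fixed effect) and institution in both primary models, and state which form institution takes. Fixed in UH3 and random in UG3 would be reasonable.
2. Add the preoperative NRS score to the pain model. State that it is a covariate and not part of the outcome, and reconcile the days 0–7 endpoint definition with the days 1–7 model.
3. Keep standardised differences for describing baseline balance, or for a labelled sensitivity analysis, and remove their role in choosing covariates for the primary analysis.
4. Use the same pre-specified model at every interim look, and take the variability estimates for the UH3 sample size from it.

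The cost is SAP wording. All the variables are already collected. The strata use about 8 degrees of freedom (2 for location, 6 for institution), negligible at N = 528; a random institution effect avoids spending the 6 in UG3. The stated N need not change.
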